4.5.17 Discharge instructions

The discharge procedure will occur upon completion of IV blood sampling. Please refer to section 5.14 for discharge instructions.

4.5.18 Estimated Total Blood Volume

Approximately 89 blood samples will be obtained throughout the course of the respective visits in addition to the blood sample required for dexamethasone analysis and fingersticks taken. The maximum estimated amount of blood estimated for each visit is 97 ml.

4.5.19 Estimated Visit Duration

The total duration of the inpatient visit is approximately 18 hours. The study time may be extended for glucose stabilization prior to discharge.

4.6 Sensor Accuracy (Sampling) Daytime Visits

Visit 6 – Day 30 Accuracy (Sampling) Visit (± 7 Days)

Visit 7 – Day 60 Accuracy (Sampling) Visit (± 7 Days)

Visit 8 – Day 90 Accuracy (Sampling) Visit (-3/+7 Days)

	Approximate Visit	Approximate Sampling
Visit 6 (Day 30 ± 7 Days)	14 hours	12.5 hours
Visit 7 (Day 60 ± 7 Days)	14 hours	12.5 hours

Visit 8 (Day 90 -3/+7 Days)	15 hours	12.5 hours
-----------------------------	----------	------------

Approximate visit timeline:

Approximate time	Activity	Time relative to first IV sample
~07:00	Admission	T=0 -1:00
~07:15-07:45	Period for glucose stabilization and CGM calibration	T=0 -0:45 - -0:15
~08:00	First IV blood sample drawn	T=0 0:00
~08:00 – 13:00	
For qualifying subjects, hypoglycemia challenge to achieve hypoglycemia target <60 mg/dL.
 
 Sampling q 5 min when glucose \leq 75 mg/dL. Target 24 YSI values <75 mg/dL including 6 YSI values <60 mg/dL at q 5 min before rescue. Subjects fed low glycemic meal. 	T=0 0:00 – +5:00
~08:00 – 13:00	
 Alternatively, for qualifying subjects, hyperglycemia challenge to achieve hyperglycemia to goal glucose >350 mg/dL. Sampling @ 5 min when glucose \geq 325 mg/dL, with a target duration of 1 hour. Challenge may be stopped once 12 samples ≥ 325 mg/dL are collected. 	T=0 0:00 – +5:00
~08:00 – 13:00	For those subjects not following a basal/bolus routine on MDI or CSII, glucose control will be free range.	T=0 0:00 – +5:00
~09:00	Fingerstick blood glucose	T=0 +1:00
~10:00	Fingerstick blood glucose	T=0 +2:00
~11:00	Fingerstick blood glucose	T=0 +3:00
~12:00	Fingerstick blood glucose	T=0 +4:00
~13:00	Fingerstick blood glucose	T=0 +5:00
~13:00-16:00	Recovery Period with meal/bolus and glucose stabilization	T=0 +5:00 - +8:00
~16:00-19:30	Free range glucose control	T=0 +8:00 - +11:30
~14:00	Fingerstick blood glucose	T=0 +6:00
~15:00	Fingerstick blood glucose	T=0 +7:00

Approximate time	Activity	Time relative to first IV sample
~16:00	Fingerstick blood glucose	T=0 +8:00
~17:00	Fingerstick blood glucose	T=0 +9:00
~18:00	Fingerstick blood glucose	T=0 +10:00
~19:00	Fingerstick blood glucose	T=0 +11:00
~19:30-20:30	Discharge preparation period	T=0 +11:30 - +12:30
~20:00	Blood draw for dexamethasone	T=0 +12:00
~20:30	Last IV blood sample drawn	T =0 + 12:30
21:00	Discharge	T=0 +13:00

The following procedures/instructions will be followed for accuracy (sampling) daytime visits at days 30, 60 and 90:

4.6.1 Pre-visit phone call

One to two days prior to the Accuracy (Sampling) Visit, site personnel will contact the subject to ensure the subject is in compliance with study device wear. Subjects may also be advised of the scheduled challenge type and will be given appropriate instructions regarding pre-visit medications and meals.

4.6.2 Device preparation

All Study devices will be time synchronized and checked for function as described in section 5.3.

4.6.3 Medications and Medical Supplies

Medications and medical supply status will be checked as described in Section 5.2.

4.6.4 Meals

Specific information regarding subject meals is described in Section 5.13. Food and drink will be controlled as required.

4.6.5 Subject Instructions prior to admission

Prior to admission, subjects should take morning medications and meals as usual as follows:

- If challenge subjects need to eat or take insulin for safety reasons, they should inform study staff of this information on arrival to the clinic.
- Subjects participating in hypoglycemia challenges should arrive fasted for 6 hours and should not take subcutaneous bolus insulin 3-4 hours previous to the challenge. Subjects should take their normal dose and timing of basal insulin.
- If subjects blood glucose is <80 mg/dL they should be instructed to eat a snack prior to

coming to the clinic, and be given specific instructions how to modify basal infusion until they arrive at the study site. Subjects may receive guidance from study staff trained in diabetes treatment regarding insulin and carbohydrate intake prior to the visit.

- Subjects should consume the food they would normally consume to treat or prevent hypoglycemia at the blood glucose level they feel is appropriate.

A clinician trained in the treatment of diabetes should also discuss and make recommendations about each subject's insulin regimen for the remainder of the day to prevent post-visit rebound hypoglycemia which can occur 12 hours later.

4.6.6 Subject Admission

The subject will arrive at the clinic during the day, no later than approximately 07:00 am and the following tests will be performed to confirm eligibility for participation in visits 6, 7 and 8:

- Hematocrit will be assessed using local lab or Point of Care testing device. Subject must be within reference range to participate in accuracy (sampling) visit.
- Female subjects of childbearing capacity will perform a urine pregnancy test. If positive, the subject will discontinue study participation. Subject withdrawal will be documented.
- The study team will confirm the absence of a febrile or vomiting illness within 24 hours of the admission.
- The study team will confirm that the subject brought his/her personal insulin and insulin pump or injection supplies (as applicable) and regular medications. The subject will continue to use his/her diabetes treatment regimen throughout the admission. The subject will be rescheduled if he/she did not bring his/her regular medications or appropriate medications are not available at the clinic.
- Clinical staff to confirm that the subject is wearing the transmitters and that the transmitters and hand held device are in communication and functioning.
- The subject will be rescheduled if he/she did not bring his/her Transmitters and cannot make them available during the visit.
- If all admission readiness criteria are not met, the subject will be rescheduled. If all of the admission readiness conditions are met, the subject will be admitted to the Clinical Research Unit.

4.6.7 Adverse events

Upon admission subject will be asked about any adverse events or changes in medication since the last study visit. The sensor insertion site will be examined. Adverse events including those associated with the insertion site will be documented on the appropriate eCRF.

4.6.8 Ketone testing

On arrival to the clinic, subject blood ketones should be evaluated from capillary blood using the ketone meter. If ketones are present, ketone testing should be repeated as described in Section 5.8 and subjects should be treated for ketones following ketone treatment guidelines Section 7.1.5.

4.6.9 SMBG testing

During in-clinic days, subjects should continue testing blood sugar using the study-supplied Subject SMBG Meter following the schedule for each visit (hourly except during overnight). For home use periods, it is requested that subjects test approximately 7 times per day (before meals, 2 hours after meals, and at bedtime). Subjects should test their blood sugar using the study supplied Subject SMBG Meter at least 2 times per day while participating in the study.

4.6.10 IV placement

Intravenous access appropriate for blood drawing and potential intravenous DW10 rescue will be established following the IV placement guidelines (Section 5.9)

4.6.11 Blood sampling for glucose measurement

Once IV access has been established, blood will be sampled for bedside reference glucose every 5-15 minutes per the Blood Sampling guidelines (Section 5.9).

4.6.12 Calibration (Visits 6, 7 & 8)

Subjects/clinicians will calibrate the system during the time period for glucose stabilization and will calibrate again approximately 12 hours later. The morning calibration reminder, adjusted through use of the HHD and mobile medical application will be set to approximately 12 hours after the evening calibration entry.

4.6.13 Glucose Challenges

Qualifying subjects will participate in hyperglycemia or hypoglycemia challenges during the times indicated in the visit timeline table. The intention of the hypoglycemia and hyperglycemia challenge is to safely manipulate the subject's blood glucose levels so that sensor performance can be evaluated over a wider range than might otherwise be observed. Details regarding the glucose challenges can be found in Section 5.12.

4.6.14 Observation subjects

Subjects with gastroparesis or those subjects unable to participate in glucose challenges will participate in the sampling sessions using free range glucose control.

4.6.15 Dexamethasone blood draw

Blood sample will be drawn at the end of the visit prior to discharge for Dexamethasone measurement. All samples will be collected and processed as described in the operations manual.

4.6.16 Discharge instructions

The discharge procedure will occur upon completion of IV blood sampling. Please refer to section 5.14 for discharge instructions.

4.6.17 Estimated Total Blood Volume

Approximately 59 blood samples will be obtained throughout the course of the respective visits in addition to the blood sample required for dexamethasone analysis and fingersticks taken. The maximum estimated amount of blood estimated for each visit is 65 ml.

4.6.18 Estimated Visit Duration

The total duration of the inpatient visit is approximately 14-15 hours. The study time may be extended for glucose stabilization prior to discharge.

4.7 Visit 8, Day 90 Sensor Removal

Sensors will be removed after glucose sampling is complete approximately 90 days post insertion, or when the designated time for Sensor removal is reached. If designated time for sensor removal is reached prior to Visit 8, the sensor will be removed at the subject's next scheduled visit or at an unscheduled visit. All Visit 8 procedures will be performed as applicable. Removal of the sensor may also be scheduled after Visit 8 if more convenient for subject and clinicians (but no longer than 100 days post insertion) provided that the Subject's transmitters and HHD have been taken from the Subject at the conclusion of Visit 8. Sensor removal before or after Visit 8 will not be considered a protocol deviation provided that removal is performed prior to 101 days post insertion and Visit 8 removal procedures/activities are followed. Subjects will be asked to complete a questionnaire regarding their experiences at the end of sensor wear period.

Blood samples will be drawn prior to sensor removal for Dexamethasone measurement. All samples will be collected and processed as described in the operations manual.

Prior to Sensor removal, the Investigator will assess the Sensor location, including by process of palpation. The Sensor will be removed following the procedure in the Eversense CGM Sensor Insertion and Removal Instructions and the Study Operations Manual.

The removed Sensors will be handled in compliance with institution/regulatory requirements for biomedical waste, and will be returned following Senseonics instructions, using the provided Biohazard Return Kit.

4.8 Visit 9 –Follow-up Visit (10 days following sensor removal. Window: sensor removal date +7 to 17 Days)

The healing of the Sensor sites will be evaluated at this planned final visit. If Sensors are removed at a time other than Visit 8, the Follow-up Visit will occur in approximately 10 days after Sensor removal.

If there is a concern by the investigator about healing of the Sensor sites, the subject will be asked to return in approximately 10 days, and followed until resolution. Any adverse event would be reported.

Subject will exit the study after the Follow-up Visit is completed as above. Subjects will continue to follow their diabetes care routine according to their health care provider recommendations.

5 GENERAL CONSIDERATIONS FOR STUDY VISITS

5.1 Definition of Enrollment

A subject is considered enrolled in the clinical trial after he or she has provided informed consent.

Subjects who fail one or more of the eligibility criteria are considered screen failures. Subjects who withdraw consent or are withdrawn by the investigator after enrollment and prior to the first Sensor insertion attempt are “withdrawn prior to Sensor insertion” and are withdrawn from the study without data acquisition. A listing of screen failures and “withdrawals prior to Sensor insertion” subjects including the reason for study exit will be reported.

Subjects who begin a first Sensor insertion procedure (defined as injection of local anesthetic) remain enrolled in the study and will be analyzed as evaluable subjects per the description of study populations in Section 11 Statistical Methods.

5.2 Medications and medical supplies

All medications and medical supplies required for the Clinical Research Center (CRC) hypoglycemia and hyperglycemia treatment protocols will be readily available at the time of subject treatment including a code cart. The subject will be rescheduled if he/she did not bring his/her required medications or appropriate medications are not available at the clinic.

5.3 Device setup

5.3.1 Device Calibration

Prior to subject blood sampling, the CRC study equipment (YSI glucose analyzer, ketone meter and study-supplied Subject SMBG Meter) will be checked for proper function and the appropriate quality controls will be run per the manufacturer's guidelines and/or Study Operations Manual, as appropriate.

5.3.2 Time sync

At each study visit the date and time on all study devices (i.e. study clocks, laptop(s), Subject SMBG Meter, Reference instrument and Senseonics Continuous Glucose Monitoring System) will be synchronized at the start of the visit to the Official US Time using www.time.gov or to an equivalent atomic clock. The details of the time and date synchronization are described in the Study Operations Manual.

The study devices do not all automatically adjust for daylight savings time. Subjects should not adjust the study device times on their own – they should wait until someone at the clinic can adjust the time so any offsets can be documented in order to reconcile the data.

5.3.3 Downloading devices

The study issued Subject SMBG meter and the sensor transmitters will be downloaded at the end of each sensor accuracy visit (visits 3-8) or at any unscheduled visit as appropriate. Sensor transmitter data will also be uploaded to a data management system to monitor calibration compliance.

5.4 Measurement Devices – Maintenance/Control Testing

At device disbursement or as appropriate, study equipment (bedside YSI glucose analyzer, ketone meter and study-supplied (SMBG) meter) will be checked for proper function and the appropriate quality controls will be run per the manufacturer's guidelines.

5.4.1 Bedside YSI

The primary instrument for plasma glucose measurements is the YSI glucose analyzer (2300 Stat Plus Glucose & Lactate Analyzer, Yellow Springs Instruments, Yellow Springs, OH, USA). Manufacturer instructions for operation, calibration, quality control, and maintenance will be followed.

5.4.2 Subject SMBG Meter

The study will supply and use a widely-used, commercially available FDA-approved self-monitoring blood glucose (SMBG) meter and strips. Control solution testing of the meter/strips will be verified with the control solution(s) specific to the meter and strips. The tested control solutions must read within the established range on the glucometer strips per

manufacturer labeling in order to be used in the study. Manufacturer instructions for operation and quality control will be followed. Subjects will be advised to perform control solution testing each time a new package of strips is deployed, or any time the subject suspects improper performance of the meter.

5.4.3 Ketone meter

The study will supply and use an FDA-approved self-monitoring ketone meter and strips (Abbott Precision Xtra or similar), which will measure β -hydroxybutyrate (β -HOB). Ketone meters will remain at the clinical site (not disbursed to the subject). Calibration of the ketone meter will be verified with the control solution(s) specific to the meter and strips. The tested control solutions must read within the established range on the strips per manufacturer labeling in order to be used in the study. Manufacturer instructions for operation and quality control will be followed.

5.5 Senseonics Continuous Glucose Monitoring (CGM) System Calibration

The Senseonics Continuous Glucose Monitoring (CGM) System will be calibrated and maintained per Eversense CGM User Guide. After the initialization period (approx. 30 hours after sensor insertion), the system enters the Daily Calibration phase. For this study, subjects should follow the recommendations below:

5.5.1 At home

During periods of home use, it is recommended to calibrate the Senseonics CGM System using SMBG values from the study-supplied meter two times per day. Calibration is best done when glucose is neither rapidly rising nor falling. Subjects can set morning and evening daily calibration reminders and Subjects will be periodically prompted by the Senseonics CGM System until a calibration point is entered.

5.5.2 In clinic

During the in-clinic sampling sessions, subjects will be instructed to calibrate at the start of the sampling session and then approximately 12 hours later unless in the initialization phase.

5.6 Use of Study Devices for Diabetes Treatment

For the duration of the study, all diabetes care decisions will be based on reference blood glucose values or SMBG as appropriate, rather than Senseonics CGM System results.

5.7 Fingersticks

During the study, while at home and in the clinic, it is requested that all subjects test their blood sugar using the study supplied SMBG meter approximately 7 times per day (before meals, 2 hours after meals, and at bedtime). Subjects should test their blood sugar using the study supplied Subject SMBG Meter at least 2 times per day while participating in the study.

All fingersticks for capillary blood glucose testing will be preceded by hand washing (with soap, warm water and a dry towel), or by using an alcohol swab and allowing the area to air dry.

5.8 Ketones

Ketone (β -hydroxybutyrate (β -HOB)) measurements will be made using a study supplied FDA-approved self-monitoring ketone meter and strips as described in 5.4.3. Subject blood ketones should be evaluated from capillary or venous blood using the ketone meter while in the clinic for sensor insertion and accuracy (sampling) visits at the following times:

- On arrival to and at discharge from the clinic
- Glucose ≥ 300 mg/dL (measure approximately within 20 minutes of the first glucose reading >300 mg/dL and repeat approximately every 60 minutes until < 300 mg/dL)
- Ketones ≥ 0.6 mmol/L (repeat approximately every 60 minutes until < 0.6 mmol/L)
- Subject has nausea, vomiting or abdominal pain regardless of glucose level.

Treatment guidelines for ketones can be found in section 7.1.5.

5.9 IV/Blood Draw Guidelines

5.9.1 IV Placement/Setup

IVs for blood sampling may be placed in the arm or hand. IV Access will be maintained during the sampling portion of the study for blood sampling and for the treatment of severe hypoglycemia or hyperglycemia during the study. If an IV fails, a reasonable effort should be made to replace it.

It is advised that sites use a heating pad in order to help keep IV sampling sites patent and improve blood flow.

Sites will be advised to use a dual stopcock closed-loop or single stopcock blood-wasting technique, as long as site personnel are cognizant of the following:

- The single-stopcock technique has a lower risk of diluted samples, but sites must take care not to exceed the protocol total blood loss limit of 475 ml in any 8-week period.
- Please note that when calculating waste volume to consider the volume of saline in the system that is drawn when clearing the line. This could include the extension set (0.2 ml), stopcock (0.2 ml), and cannula (0.1 ml). Therefore a 1.5 ml “waste” draw actually contains 1.0 ml blood.

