4.3 Subset of subjects for dexamethasone analysis

A designated subset of a minimum of 6 and a maximum of 9 subjects across the study will return on days 3-6 for blood draws (~ 4 mL each) for dexamethasone analysis. These samples are in addition to the samples collected at visit 3 on days 1 and 2 and at visit 4 on days 7 and 8 (as described below).

Dexamethasone results from these subjects will be used to determine whether and when the remaining subjects will need to come in for an additional blood draw for dexamethasone measurement. This may occur within several hours of sensor insertion (at the end of Visit 2), or during the first 7 days post sensor insertion.

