5.9.3 Sample volume

Approximately 1.0 ml IV blood samples will be collected (after saline is cleared from sampling apparatus) in sample containers with an appropriate anticoagulant additive (BD Microtainer K2E tubes (REF 365955) or Sarstedt Monovette with K2E (REF 06.1664.001) or similar) for analysis.

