6 CLINICAL LABORATORY EVALUATIONS AND ESTIMATED BLOOD VOLUMES

Standard clinical laboratory analysis equipment, procedures and quality control will be used for all laboratory evaluations in this clinical trial. Blood samples will be drawn at Visits 1 through 8 (or sensor removal as appropriate) for laboratory dexamethasone measurement. Additionally designated subjects across the study will have blood samples drawn for dexamethasone

measurement 3 times on the insertion date, and on each day between visits 3 and 4. Samples for hemoglobin A1C measurement will also be collected at Visit 1, 6, 7 and 8. Hematocrit will be assessed using local lab or Point of Care testing device.

Total Estimated Blood Loss

Maximum estimated blood loss over the study is 504 mL.

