8.2.3 Risks Associated with Participation in the Clinical Investigation

This clinical investigation involves subjects with diabetes mellitus. These subjects may experience hyperglycemia and hypoglycemia as a consequence of their existing condition and medical management (e.g. insulin administration). For this study, hyperglycemia and hypoglycemia will not be reported as adverse events unless meeting criteria of a Serious Adverse Event. Episodes of hyperglycemia and hypoglycemia as documented by the Subject SMBG Meter will be reported in an extra listing separate from the AE listings. Should a known side effect(s) occur to administered medication(s) used in the intervention, such effects will be reported as part of the adverse event description and will not be considered a separate adverse event.

The amount of blood drawn for in-clinic testing during the study is below the acceptable limits of blood donation of approximately 475 mL; hence it does not pose any additional unacceptable risk to the subjects.

This clinical investigation involves the following procedures that present risk: placement of an intravenous catheter, frequent blood sampling, and conduct of hyperglycemia and hypoglycemia challenges at the clinic visits. In addition, Subjects in this study may use an insulin pump or syringes to administer subcutaneous insulin.

The following risks are potentially associated with such procedures:

- Routine administration of insulin may cause hematoma, redness, swelling and itch at the injection site, skin rash, itch, sweating, gastro-intestinal complaints, edema, difficulty breathing, palpitations and drop in blood pressure, and even death.
- Hypoglycemic symptoms requiring medical intervention which may include seizures, neuroglycopenia, coma and even death (including occurrence during home use)
- Insulin administration leading to hypoglycemia include: cold sweating, cool and pale skin, fatigue, nervousness, shakiness, anxiety, weakness, confusion, feeling of numbness, hunger, impairment of vision, problems with concentration, headache, nausea, palpitations, coma, or death.

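### The stated maximum blood volumes count neither discarded blood nor the subset's days 3–6 draws, so they do not show when permitted blood-wasting sampling would pass 475 mL in 8 weeks

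*Protocol*

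**What the plan says.** Protocol Section 5.9.1 lets sites use a dual-stopcock closed loop or a single stopcock with wasted blood. It adds that with the single stopcock "sites must take care not to exceed the protocol total blood loss limit of 475 ml in any 8-week period". It also explains how to allow for saline when working out waste: in its example, a 1.5 mL waste "draw actually contains 1.0 ml blood". Section 5.9.3 treats the retained sample as separate from the clearing draw: "Approximately 1.0 ml IV blood samples will be collected (after saline is cleared from sampling apparatus".

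The volumes appear in several places:

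- Section 4.5.18 (Visits 4 and 5; Section 4.4.16 gives the same for Visit 3): "The maximum estimated amount of blood estimated for each visit is 97 ml".
- Section 4.6.17 (Visits 6–8): "The maximum estimated amount of blood estimated for each visit is 65 ml".
- Section 6: "Maximum estimated blood loss over the study is 504 mL".
- The visit table in Protocol Section 4 and SAP Table 1 carry the same 97, 65 and 504 mL.

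In Section 4.3, a subset of 6 to 9 subjects "will return on days 3-6 for blood draws (~ 4 mL each) for dexamethasone analysis". The risk statement in Section 8.2.3 reads: "The amount of blood drawn for in-clinic testing during the study is below the acceptable limits of blood donation of approximately 475 mL".

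**The concern.** A figure labelled as a maximum should cover every technique the protocol permits. If these maxima leave out discarded blood, a site that plans from them cannot see how much of the 475 mL allowance the single-stopcock technique uses, or at which visit it runs out. The limit protects subjects, and Section 8.2.3 rests its statement of no additional unacceptable risk on staying below it. A site that reached the limit partway through the schedule would have to change technique, shrink its discards, exceed the limit or give up reference samples. The visits affected are those up to Day 30, and SAP Section 4.4 gives accuracy data through Day 30 as one reason for the agreed sample size.

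**Working it through.** **Inputs.** Glucose samples are 1.0 mL each (Section 5.9.3), with 89 at each of Visits 3–5 and 59 at each of Visits 6–8. Dexamethasone draws are 4.0 mL: three at Visit 2 in the subset and one in other subjects (Section 4.2.4), two at each of Visits 3–5, and one at Visit 1 and at each of Visits 6–8. A1C draws are 2.0 mL at Visits 1, 6, 7 and 8.

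**1. Reproduce the stated figures with no discards.**

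- Visit 1: 4 + 2 = 6. Visit 2 (subset): 3 × 4 = 12.
- Visits 3–5: 89 × 1.0 + 2 × 4.0 = 97 each.
- Visits 6–8: 59 × 1.0 + 4 + 2 = 65 each.
- Total: 6 + 12 + 3 × 97 + 3 × 65 = 504.

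Every figure matches, which leaves no room for discarded blood. The total takes the subset's 12 mL at Visit 2 but not the same subset's days 3–6 draws: 504 + 4 × 4 = 520 mL.

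**2. Closed-loop sampling within 8 weeks.** Volumes outside the accuracy visits run from 4 mL (non-subset, Visit 2 only) to 34 mL (subset: 6 + 12 + 16, with Visit 1 inside the period).

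- Through Visit 6 (Day 37 at the latest): 4 + 291 + 65 = 360 to 34 + 291 + 65 = 390 mL.
- If Visit 7 falls in the same 8 weeks (its window opens on Day 53): 425 to 455 mL.

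Both fit within 475 mL.

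**3. Single stopcock.** Assume one discard of 1.0 mL of blood per glucose sample. Each of Visits 3–5 becomes 97 + 89 = 186 mL, and each of Visits 6–8 becomes 65 + 59 = 124 mL. The whole study becomes 504 + 3 × 89 + 3 × 59 = 948 mL (964 in the subset).

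| Samples per visit (Visits 3–5 / Visit 6) | After Visit 5, mL | After Visit 6, mL |
|---|---|---|
| 89 / 59, as planned | 562–592 | 686–716 |
| About 70 / 45, from Protocol 11.1.4 | 449–479 | 545–575 |
| 64 / 50, every 15 minutes throughout | 412–442 | 518–548 |

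First row: 4 + 3 × 186 = 562 and 34 + 558 = 592, then + 124. Second row: 4,632 / 66 = 70.2 and 2,965 / 66 = 44.9 pairs per sensor; 4 + 3 × (140.4 + 8) = 449, then + 95.8; the upper ends are 30 mL higher. Third row: 4 + 3 × (128 + 8) = 412, then + 106; the upper ends are again 30 mL higher.

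At planned counts the limit is crossed within Visit 5, between (475 − 34 − 372 − 4) / 2 = 32.5 and (475 − 4 − 372 − 4) / 2 = 47.5 samples, that is, at about sample 33 to 48.

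**4. Largest discard that fits, at planned counts.**

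- Through Visit 6 (326 samples): (475 − 390) / 326 = 0.26 to (475 − 360) / 326 = 0.35 mL.
- With an early Visit 7 (385 samples): (475 − 455) / 385 = 0.05 to (475 − 425) / 385 = 0.13 mL.

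**The case against.** Section 5.9.1 already deals with much of the hazard. It makes the single stopcock conditional on staff knowing about the limit, makes the limit mandatory and tells sites how to count the blood in a waste draw. A site that follows the section would count its waste and could switch technique. The 1.0 mL is an illustration of subtracting saline, not a prescribed discard, and nothing states how many discards accompany each sample. Section 5.9 refers to a Study Operations Manual for more detail; that manual is not available here and may set a discard volume or a tracking form. In SAP Table 1 the blood-volume row carries a footnote mark whose text is not in the copy reviewed, so a qualification there cannot be ruled out.

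Most of this stands, and it makes any breach conditional on technique and discard volume. It does not make the stated maxima right for a permitted technique, supply the subset's missing 16 mL or reconcile Section 8.2.3 with Section 6.

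A reader might also infer that 504 mL against 475 mL is itself a breach. It is not: the limit applies to any 8-week period, and 504 mL spans the whole study.

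**Conclusion.** The maxima are incomplete as written. They count retained blood only, and the total is 16 mL short for the subset, whose maximum is 520 mL before any discard. The statement in Section 8.2.3 is correct only per 8 weeks with closed-loop sampling. These three findings need no assumption about discards.

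The size of the possible excess does need one. At one 1.0 mL discard per sample, 475 mL is passed during Visit 5 at planned counts and by the end of Visit 6 at all three sample counts examined. Closed-loop sampling, or sufficiently small discards, stays within the limit.

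A reader might conclude that the trial will exceed its safety limit, or will lose Day 14 or Day 30 reference data. The documents support neither. They do not say which sites use the single stopcock or how much they discard, so neither the chance of a breach nor any data loss can be estimated. This is a correction that should be made to figures behind a safety limit, with a modest operational control added.

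**What to change.** 1. **Volumes.** In the Protocol visit table, Sections 4.4.16, 4.5.18, 4.6.17 and 6, and SAP Table 1, label the maxima as excluding discards. Give single-stopcock figures alongside: 186 mL, 124 mL and 948 mL at 1.0 mL per discard. Add 16 mL for the dexamethasone subset.
2. **Risk statement.** Reword Section 8.2.3 as an 8-week closed-loop figure: up to 390 mL through Visit 6, and up to 455 mL if an early Visit 7 falls in the same 8 weeks.
3. **Control.** In Section 5.9.1, require a running 8-week blood-loss total per subject that includes discards, and closed-loop sampling whenever the projected total would pass 475 mL. In practice that means Visits 3–6, and Visit 7 when it is within 8 weeks of Visit 3.

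A fixed cap on discard volume is a poor substitute: with an early Visit 7 only about 0.05–0.13 mL per sample fits.

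The cost is wording, corrected table entries, a line on the visit worksheet and dual-stopcock sets at sites without them. No subjects or visits are added. The downside is that Section 5.9.1 credits the single stopcock with a lower risk of diluted samples, so more closed-loop sampling may mean some rechecks.
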